Human genome wide association studies have revealed novel genetic loci associated with coronary heart disease. One such locus resides in *LNK/SH2B3* which in mice is expressed in hematopoietic cells and suppresses thrombopoietin signaling via its receptor MPL. Using human cord blood, we recently showed that the common TT risk genotype (R262W) of *LNK* is associated with expansion of hematopoietic stem cells and enhanced megakaryopoiesis, demonstrating reduced LNK function and increased MPL signaling. To model the human reduced LNK function associated with the TT risk genotype, we used *Lnk*-/- mice. In mice, hematopoietic *Lnk* deficiency led to accelerated arterial thrombosis, but only in the setting of hypercholesterolemia. In platelets LNK deficiency increased MPL signaling, while cholesterol loading decreased SHIP-1 activation, acting convergently to increase AKT and platelet activation. Increased platelet activation combines with hypercholesterolemia induced myelopoiesis to promote pro-thrombotic platelet/leukocyte aggregate formation and accelerated atherogenesis. Atherosclerotic lesions were characterized by larger size, increased necrotic cores and increased leukocyte-derived DNA nets.

These findings suggest the possibility that in humans, the common LNK variant rs3184504 impacts platelet activation in a fashion dependent on plasma cholesterol levels. In light of these findings, we propose the following studies as an investigator initiated study. The primary goal is to assess the impact of Evolocumab therapy on platelet function of FH patients in a randomized, double blind study. The secondary goal is to determine if platelet activation or the response to Evolocumab therapy is modified by rs3184504 polymorphism. We believe that these investigations will complement ongoing studies to demonstrate that Evolocumab reduces athero-thrombotic risk and aid the decision-making as to whether Evolocumab can reduce the atherothrombotic risk in ACS patients.

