#### **Proposed studies.**

- A. Sample collection: All adult male and female subjects who have a clinical diagnosis of familial hypercholesterolemia (FH) and who are referred to [name] Practice for treatment with PCSK9 inhibitor, with LDL cholesterol levels  $\geq 70$  mg/dl on baseline

treatment with statins and/or ezetimibe or intolerant to statin and/or ezetimibe. The platelet counts in peripheral blood should be  $\geq 100,000$  per microliter. The subjects that meet these criteria will be recruited for the study.

Blood will be collected as shown in Fig. 1 in the morning from the resting and fasting subjects. An aliquot will be collected for genomic DNA and platelet-rich plasma (PRP) preparation.

B. Power Calculation:

The effect of PCSK9

inhibitors, including evolocumab, on platelet activation measures has not been assessed previously. However, our hypothesis is based on the LDL-cholesterol lowering effect of evolocumab, and evolocumab has been demonstrated to have at least as potent an effect on LDL lowering as statins. Statin therapy in hypercholesterolemia patients results in 50% reduction in LDL-cholesterol levels and add-on evolocumab therapy indicated an additional 50-60% reduction. Therefore, we base our power estimates on platelet activation data available for statins.

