Primary measure/platelet aggregation - The primary measurement will be ADP-stimulated platelet aggregation as assessed by the commercially-available VerifyNow P2Y12 assay (Accriva Diagnostics). The assay read-outs are 1) PRU, platelet reactivity units (specific for P2Y12 receptors); 2) BASE, total platelet function despite P2Y12 receptor blockage; and 3) IPA, percent platelet P2Y12 inhibition calculated as  $[(\text{BASE} - \text{PRU}) / \text{BASE}] \times 100$ . Two reports involving patients on antiplatelet therapy with high residual platelet reactivity demonstrated an effect of statins on lowering platelet aggregation via the VerifyNow assay. In CAD patients treated with clopidogrel, the addition of atorvastatin for 30 days resulted in an absolute mean difference of  $102 \pm 54$  PRU compared to baseline, corresponding to a  $37 \pm 14\%$  IPA. In a separate study of CAD/diabetic patients treated with clopidogrel, the addition of atorvastatin for 30 days resulted in an absolute mean difference of  $106 \pm 75$  PRU compared to baseline, corresponding to a  $33 \pm 20\%$  IPA. Similar effect sizes and variabilities of statins on reductions in platelet aggregation were observed in type II

Step	Procedure
1	Venipuncture with G21 butterfly needle.
2	Collect 2 ml blood into sodium citrate tube as waste tube
3	Collect 3x2 mL blood into 3 Greiner Vacuette tubes containing 3.2% sodium citrate. For VerifyNow assays.
4	Collect 2x3 ml blood into 2 Greiner Vacuette tubes containing 3.2% sodium citrate. For platelet activation assays.
5	Collect 1x2 ml blood into Vacuette tube containing EDTA. For CBC assay.
6	Collect 2x2 ml blood for metabolic panel, lipid panel and TSH assays.
7	Collect urine for urinalysis.
8	Pregnancy test with stick assay.

hyperlipidemic patients using light transmittance aggregometry. The relative reductions were reported as  $30 \pm 23\%$  (pravastatin),  $19 \pm 16\%$  (atorvastatin), and  $22 \pm 22\%$  (simvastatin).

[figure not shown]

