Secondary measures – Secondary measures will include various cellular and circulating markers of platelet activation measured by flow cytometry or commercially-available enzyme-linked immunoassays (ELISAs). The target enrollment of 24 subjects should provide at least 80% power to detect differences between treatment groups based on data reported in the literature. For example, platelet P-selectin level measured by flow cytometry and reported as % positive cells (out of 50,000 cells counted) showed a mean reduction  $\pm$  SD of  $10.9 \pm 6.0$  (simvastatin),  $10.9 \pm 5.6$  (atorvastatin),  $7.2 \pm 6.8$  (fluvastatin) and  $9.0 \pm 6.8$  (pravastatin) following 30 days of statin treatment in hypercholesterolemic patients compared with untreated controls. In a separate study of stroke patients with hypercholesterolemia, platelet P-selectin showed a mean reduction of  $41 \pm 27\%$  positive cells in response to thrombin following 6 months of treatment with simvastatin compared to baseline measurements in the same subjects before statin treatment. An additional

effect of simvastatin treatment was observed for soluble P-selectin serum concentrations measured by ELISA. Soluble P-selectin showed a mean reduction of  $46.4 \pm 49$  ng/ml compared to baseline measurements in the same subjects before statin treatment. Other secondary measures include VerifyNow IIb/IIIa and VerifyNow Aspirin assays.

C. Study Design: Amgen will provide Evolocumab and placebo as open label. An independent biostatistician will generate a randomization table and provide it to Research Pharmacy of CUMC and Research Pharmacy will randomize the subjects accordingly. All patients recruited will start with placebo and blood and urine samples will be collected at day 7 and day 14. Then, the subjects will be randomized so that half will continue to receive placebo and half will receive Evolocumab via subcutaneous injection of 140 mg every 14 days. Blood and urine samples will be collected at day 21 and day 28. Then, all patients will receive Evolocumab 140 mg every 14 days and the treatment will continue.

Blood and urine samples will be collected following Evolocumab therapy at day 84 and 196 (Fig. 2). While every effort will be made to collect the blood and urine samples on the indicated time points, variation for the sample collection within 1-3 days at the indicated time point will be

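### The plan claims a double blind but assigns no masking step, and lipid results drawn in the randomised period can disclose the arm to anyone who sees them

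*Combined protocol and SAP*

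**What the plan says.** The Introduction gives the primary goal as to "assess the impact of Evolocumab therapy on platelet function of FH patients in a randomized, double blind study".

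Under Proposed studies, section C (Study Design), the supply is described in one sentence: "Amgen will provide Evolocumab and placebo as open label". The next sentence covers allocation: "An independent biostatistician will generate a randomization table and provide it to Research Pharmacy of CUMC", and "Research Pharmacy will randomize the subjects accordingly". Everyone starts on placebo, with samples at days 7 and 14. After that, "the subjects will be randomized so that half will continue to receive placebo and half will receive Evolocumab". Samples follow at days 21 and 28, and then all subjects receive evolocumab.

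The blood-collection table in section B includes the step "Collect 2x2 ml blood for metabolic panel, lipid panel and TSH assays", with no visit excepted. Section E also lists plasma LDL cholesterol among the study assays. On the expected size of the lipid effect, section B says that "add-on evolocumab therapy indicated an additional 50-60% reduction".

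The text does not say who is masked, whether the pharmacy masks or relabels syringes, who injects, who receives lipid results during the randomised period, or whether assay operators are masked.

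**The concern.** Product that arrives identifiable is masked only if someone is given the task of masking it. The plan gives the pharmacy the task of randomising and says nothing more.

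Separately, the drug has a large effect on a routine laboratory value that is measured in every subject while the comparison with placebo is running. Samples at days 7 and 14, when all subjects are on placebo, supply each subject's own reference value. Anyone who sees the day-21 result beside it can make a good guess at the arm, however well the syringes are masked.

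Knowledge of the arm could influence:

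- whether a platelet reading is repeated or rejected;
- how flow cytometry is read;
- whether partial data from a dropout are used, since section C leaves some discretion once day-28 data exist;
- what subjects do between days 21 and 28.

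The planned comparison has about 11 subjects per arm, so each subject carries roughly 1/11, or 9%, of an arm mean.

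**Working it through.** **The plan's own figures.** The plan states no figure on blinding. Its nearest computed figure is the group size. A two-sided paired t-test at alpha 0.05 with a mean difference of 51 PRU and an SD of 54 PRU needs 11 subjects (power 0.806 by the noncentral t), which matches section B. This only confirms the group size used here; the blinding point does not depend on it.

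**How well one LDL value identifies the arm.** Inputs:

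- Expected LDL fall on evolocumab, R: 50-60% (section B).
- Change on placebo: 0% (assumed).
- SD of the percent change within an arm, s: 10-30 percentage points (assumed; the documents give none).
- Full effect present at the sample (assumed). Day 21 is 21 − 14 = 7 days after the switch, and day 28 is 14 days after.
- Allocation 1:1 (section C), so chance is 50%.

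With normal distributions, a common SD and a cut at half the expected fall, the proportion identified correctly is Φ(R / 2s).

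| s (points) | R = 50 | R = 60 |
|---|---|---|
| 10 | Φ(2.50) = 0.994 | Φ(3.00) = 0.999 |
| 15 | Φ(1.67) = 0.952 | Φ(2.00) = 0.977 |
| 20 | Φ(1.25) = 0.894 | Φ(1.50) = 0.933 |
| 25 | Φ(1.00) = 0.841 | Φ(1.20) = 0.885 |
| 30 | Φ(0.83) = 0.798 | Φ(1.00) = 0.841 |

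The range is about 80-99%. In 22 subjects that is about 18 (22 × 0.798 = 17.6) to 22 identified correctly, against 11 by chance.

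If only half the effect were present at day 21 (R = 25-30, for illustration), the same formula runs from Φ(25/60) = 0.66 at s = 30 to Φ(30/20) = 0.93 at s = 10. Disclosure is then weaker but still better than chance.

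**Which panel can come before which result.** If the primary reading is at day 28, the lipid tubes and the VerifyNow tubes come from the same draw (blood-collection table), and VerifyNow gives its result in about 10 minutes (section E). Only the day-21 panel clearly precedes that reading. The plan does not say when flow cytometry and ELISA are run or read, so a day-28 lipid result could be known before those results and before decisions on inclusion.

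**Room for bias in the primary measure.** VerifyNow is read optically by an instrument, without pipetting or sample preparation (section E). As an illustration, one repeat reading that moved a subject by a full SD of 54 PRU would move an arm mean by 54/11 = 4.9 PRU, about 10% of the 51 PRU planning effect. Several decisions in the same direction would be needed for a large shift.

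**The case against.** The strongest reply is that open-label supply to a pharmacy is not open-label administration. An independent biostatistician makes the table, Research Pharmacy holds it and randomises, and the Introduction states the intent. That arrangement is compatible with a pharmacy-held blind. This stands: a reader might infer that the trial is in effect open label, and the documents do not support that. On supply, what is missing is mainly detail.

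A reader might also infer that the lipid panels do unblind the study. No section says that subjects, investigators or assay operators see lipid results in the randomised period. The exposure comes from the plan's silence and is not a stated fact.

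A third tempting reading is that the day-28 panel compromises the primary reading. It shares the draw with a test that reports in minutes, so this is unlikely.

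Finally, the 80-99% is the accuracy of guessing the arm once LDL is seen. It is neither a bias in PRU nor the chance that anyone sees the value, and it rests on assumed SDs and timing. The 50-60% refers to therapy added to a statin, while section A also admits subjects who cannot tolerate one. All of this limits the size of the concern. It does not supply the missing protection for a blind that the plan claims.

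**Conclusion.** The point holds in a limited form. The plan promises a double blind, receives identifiable product, assigns no masking step, names no masked roles and does not restrict access to a result that would usually disclose the arm. Disclosure to someone who sees the day-21 or day-28 LDL is about 80-99% accurate, given SDs of 10-30 points, no placebo change and the full effect at sampling.

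The main exposure for a day-28 VerifyNow reading is the day-21 panel, over about seven days. The day-28 panel matters for flow cytometry and ELISA results read later and for inclusion decisions. Bias in the instrument-read primary measure is limited, and the documents do not show that any has occurred or will occur.

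This takes day 28 as the primary reading. Section B sets the primary endpoint at 30 days of treatment, whereas section C gives 14 days of randomised comparison (day 14 to day 28) before all subjects receive evolocumab. Those passages must be reconciled. Sections B and F also name different VerifyNow tests as primary, but both are instrument-read, so this point is unaffected.

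**What to change.** Add to section C:

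1. **Hold on lipid results.** Day-21 and day-28 lipid results, including LDL measured as a study assay, are withheld from subjects, investigators and assay operators. The hold lasts until that subject's day-28 platelet assays are recorded and inclusion decisions made. Results are released on request for safety.
2. **Masking statement.** Research Pharmacy dispenses masked syringes, and the plan lists who is masked through the day-28 sample. If the syringes cannot be masked, drop the double-blind label from the Introduction and state which roles are masked.

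The cost is protocol wording, a short delay in returning lipid results, and a small amount of pharmacy and laboratory work for masked dispensing and the release hold. If the ELISAs are run in batches the hold will be longer, so the plan should say when they are run. Sample size, visits and assays do not change. If masking at the pharmacy is already intended, the second item only records it.

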The reference range for the VerifyNow assay in individuals not on antiplatelet therapy is 180-376 PRU. These data are continuous and normally distributed. Thus, means and standard deviations will be used to describe reductions in platelet aggregation. Based on reported literature indicating additional effects of statins on platelet function following 30-day vs shorter periods of treatment, we have revised our experimental design to have a primary endpoint of 30-day treatment. Within-group thirty day evolocumab treatment will be tested by one-group paired t-test (two-sided) using each subject as its own control (evolocumab treatment vs vehicle pre-treatment control). Between-group thirty day evolocumab treatment will be tested by standard two-group t-test (two-sided, evolocumab vs vehicle control group run in parallel). The sample size estimates have been run using one-group, paired t-test published data. Using PRU mean difference = 102, SD = 54, power = 0.8 and alpha = 0.05, we estimate 6 subjects. Since the effects of statins on platelet aggregation may be mediated by both LDL-lowering and non-LDL-lowering mechanisms, we can calculate the sample size based on 50% reduced mean difference (PRU = 51). Then, we estimate 11 subjects. An equal number of subjects will be required for the placebo group run in parallel. Target enrollment will include all patients screened; we estimate that 10% may not be eligible based on exclusion criteria and/or may not return for scheduled blood draws. Thus, for 80% power, the target enrollment is 24 subjects over two years.

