allowed. The power of this design is that we can compare any changes due to Evolocumab therapy relative to a placebo control.

Based on the power calculations as detailed above, recruitment of total 20 participants into this study will give ~80% power for statistical significance of 0.05. We target to recruit 24 subjects over 2 year period. However, we anticipate that some participants will drop out from the study and incomplete data will be obtained. We will continue to recruit the subjects until the complete data sets for 22 subjects are obtained. Incomplete data from the dropout may not be used unless data up to 28 days at least are collected.

D. Genotyping: rs3184504 genotyping will be performed using the genomic DNA samples

and rs3184504 specific PCR genotyping primers from Invitrogen.

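### The Study Design section says 20 participants give about 80% power, but the plan's own calculation needs 22 evaluable; 20 give 75.7% at best

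*Combined protocol and SAP*

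**What the plan says.** All the figures come from the combined protocol and SAP, under Proposed studies.

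**Section B, Power Calculation (primary measure).**
- The within-group effect "will be tested by one-group paired t-test (two-sided) using each subject as its own control". A two-sided two-group t-test is also planned, against the parallel placebo group.
- Only the first test was used for sizing: "The sample size estimates have been run using one-group, paired t-test published data".
- For the full statin effect the plan begins "Using PRU mean difference = 102" and, with SD 54, "power = 0.8 and alpha = 0.05, we estimate 6 subjects".
- It then halves the effect: "we can calculate the sample size based on 50% reduced mean difference (PRU = 51). Then, we estimate 11 subjects".
- It doubles this for the placebo group: "Then, we estimate 11 subjects. An equal number of subjects will be required for the placebo group run in parallel". The total of 22 is implied at this point, not printed.
- After allowing 10% for ineligibility or missed blood draws, it concludes: "Thus, for 80% power, the target enrollment is 24 subjects over two years".

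**Section C, Study Design.** Citing the calculations in section B, it says that "recruitment of total 20 participants into this study will give ~80% power for statistical significance of 0.05". The same paragraph then sets a recruitment target of 24 and says that recruitment will go on until 22 subjects have complete data.

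**The concern.** Section C presents 20 as the outcome of section B's calculation, yet nothing in section B gives 10 per group or 20 in total. A reader who meets the sentence alone, or copies it into a report, would credit 20 participants with a power that the plan's method does not give them.

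The sentence also names no test. Section B sized the trial on the within-group paired comparison, while section C presents comparison with placebo as the strength of the design. An unqualified power figure in that paragraph can be read as covering the placebo comparison, for which the plan gives no power calculation on the primary measure.

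**Working it through.** **Inputs, all from section B:** mean paired difference 102 PRU, halved to 51; SD of the difference 54; two-sided alpha 0.05; target power 0.80; as many placebo as evolocumab subjects; 10% ineligible or lost.

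**Formula.** For a one-group paired t-test with n pairs, the degrees of freedom are n − 1 and the noncentrality is λ = (difference / SD) × √n. Power is P(|T| > t_crit), where T is noncentral t with noncentrality λ and t_crit is the 0.975 quantile of the central t.

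**Step 1: reproduce the plan's own figures.**
- At 102 PRU the ratio is 102/54 = 1.889. Power is 87.8% at n = 5 and 95.4% at n = 6, so the plan's 6 meets the target (5 would have been enough).
- At 51 PRU the ratio is 51/54 = 0.944. The results are:

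| n per group | df | t_crit | λ | Power |
|---|---|---|---|---|
| 9 | 8 | 2.306 | 2.833 | 70.0% |
| 10 | 9 | 2.262 | 2.987 | 75.7% |
| 11 | 10 | 2.228 | 3.132 | 80.6% |
| 12 | 11 | 2.201 | 3.272 | 84.5% |

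The smallest n that reaches 80% is 11, exactly the plan's figure. This is good evidence that the plan used this method.

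**Step 2: apply the same method to 20.**
- 20 evaluable, 10 per group: 75.7%, which is 80 − 75.7 = 4.3 points below 80%.
- 20 recruited with 10% lost: 20 × 0.9 = 18, or 9 per group: 70.0%, which is 10 points below.

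**Step 3: check 22 against 24.** 11 + 11 = 22 evaluable. Allowing for 10% loss, 22/0.9 = 24.4; conversely, 24 × 0.9 = 21.6. The two figures agree to rounding.

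**Step 4: the between-group t-test, conditional only.** The plan gives no SD for this comparison. Here df = 2n − 2 and λ = (difference / SD) × √(n/2). At 11 per arm and 51 PRU:
- if the SD of the compared values is 54, λ = 2.215 and power is about 56%;
- if it is 75 (the SD of the PRU change in the other clopidogrel study cited in section B), λ = 1.595 and power is about 33%.

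Both SDs are before/after SDs from statin studies. Applying them to each arm here is an assumption.

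**The case against.** The best defence is that the sentence does no work. It says approximately 80%, the shortfall is about 4 points if all 20 are evaluable, and the next sentences set a target of 24 and a rule to continue until 22 data sets are complete. At 22 the plan's method gives 80.6%. This stands, and it is why the point is minor. It does not make the sentence right: the text speaks of recruitment, and on the plan's own loss allowance 20 recruited means 70.0%.

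One could also say that 20 exceeds 80% under other methods. At 10 per group and 51 PRU, a normal approximation gives 84.8% and a one-sided t-test 86.6%. But each of these reaches 80% by 9 per group, so neither explains the plan's 11, and section B specifies two-sided tests. The full 102 PRU effect would also clear 80% easily, but the plan set that aside when it sized on 51.

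A reader might infer more than the documents support:
- *That 20, 22 and 24 are three rival sample sizes.* They are not. 22 is the evaluable number and 24 is the enrolment that allows for loss. Only 20 is out of line.
- *That 24 is too few because 24 × 0.9 falls below 22.* The gap is 0.4 of a subject, the 10% is itself an estimate, and the 22-complete rule means that 24 is not a ceiling.
- *That the trial could stop at 20 and still claim its power.* The 22-complete rule largely blocks this.
- *That the placebo comparison is shown to have about 50% power.* That figure holds only if SD 54 applies to the compared values in each arm, which the plan does not say.

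**Conclusion.** The power stated for 20 participants is wrong as written. By the calculation that the sentence cites, 22 evaluable subjects are needed (80.6%). Twenty give 75.7% with no loss and 70.0% with the plan's 10% loss. This rests on the plan's own inputs and on the two-sided paired t-test, which reproduces its figure of 11.

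The point is minor. It concerns a stated figure, and neither the recruitment target nor the rule on complete data sets depends on it. What also needs saying is that the 80% belongs to the within-group test alone. The documents do not settle the power of the between-group test, so any figure for it has to carry its assumed SD.

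**What to change.** In section C, delete the sentence on 20 participants, or replace it with: *22 evaluable subjects (11 per group) give about 81% power for the within-group paired t-test at a mean difference of 51 PRU and SD 54, two-sided alpha 0.05.* Add that this power applies to that test only and not to the between-group t-test. Keep 24 as the enrolment target and 22 as the required number of complete data sets.

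If a power for the between-group test is quoted, give it as a range with its assumption: at 11 per arm and 51 PRU, about 56% if the SD of the compared values is 54 and about 33% if it is 75.

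The cost is wording only. The stated power becomes slightly less favourable and is tied to one named test; no subjects, visits or procedures are added.

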- E. Assays: We propose to use a clinically validated system, VerifyNow, as the assay for assessment of platelet activation state. Compared with other assays, this system requires ~2 ml whole blood, with minimal ex vivo manipulations, minimal hands-on time and no pipetting or sample preparation. It is fast (10 min for result presentation) and approved as a clinical lab test of platelet reactivity. Thus, the results obtained this way should be more reliable when the data need to be compared with results from other studies using the same assay. In principle, this assay is designed to measure platelet function based upon the ability of activated platelets to bind fibrinogen. Fibrinogen-coated microparticles aggregate in whole blood in proportion to the number of unblocked platelet GP IIb/IIIa receptors. Light transmittance increases as activated platelets bind and aggregate fibrinogen-coated beads. The instrument measures this change in optical signal caused by aggregation. We propose to use VerifyNow IIb/IIIa, VerifyNow PRUtest, and VerifyNow Aspirin assays, testing platelet responses to thrombin-like peptide, ADP and arachidonic acid, respectively. In addition to the VerifyNow assay, basal level of P-selectin and active form of GPIIb/IIIa at surface of platelets will be determined by flow cytometry. In order to reduce the variation generated by manipulation of blood samples in vitro, we will use 1% paraformaldehyde to fix an aliquot of the whole blood sample and basal levels of P-selectin and active GPIIb/IIIa at surface of platelets will be determined by flow cytometry after staining with specific P-selectin or PAC-1 antibody (PAC-1 specific for active GPIIb/IIIa). Plasma levels of TAT, sP-selectin and sCD40L will be determined by ELISA assays. Levels of plasma LDL cholesterol, HDL cholesterol, triglyceride and platelet total cholesterol content will be determined. All these assays are validated assays.

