- F. Analysis: The primary hypothesis is that Evolocumab will reduce thrombin-peptide stimulated platelet activation as determined by VerifyNow. Secondary hypothesis is related to basal and ADP or arachidonic acid stimulated activation, direct measurements of platelet activation by flow cytometry or levels of the surrogate markers. This will help assess the validity of these markers for larger ongoing studies that we are performing in collaboration with Amgen using EDTA plasma samples obtained in phase 2 development studies of Evolocumab. Even though the statistical power is limited by small sample size, the potential modification of these phenotypes by rs3184504 polymorphism will be examined.

**Time Frame:** two years

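### Sections B and F name different primary endpoints (ADP-stimulated PRU and thrombin-peptide VerifyNow), and the sample size is calculated only for PRU

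*Combined protocol and SAP*

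**What the plan says.** All four statements below are current text in the combined protocol and SAP, under Proposed studies.

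- Section B, primary measure: "The primary measurement will be ADP-stimulated platelet aggregation as assessed by the commercially-available VerifyNow P2Y12 assay". The read-out used for sizing is PRU.
- Section B, secondary measures: "Other secondary measures include VerifyNow IIb/IIIa and VerifyNow Aspirin assays".
- Section F, primary: "The primary hypothesis is that Evolocumab will reduce thrombin-peptide stimulated platelet activation as determined by VerifyNow".
- Section F, secondary: "Secondary hypothesis is related to basal and ADP or arachidonic acid stimulated activation".

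Section E links assays to agonists. It lists VerifyNow IIb/IIIa, PRUtest and Aspirin, in that order, as "testing platelet responses to thrombin-like peptide, ADP and arachidonic acid, respectively". Thrombin-peptide is therefore the IIb/IIIa assay and ADP is the PRUtest (P2Y12) assay.

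The sample size in Section B starts from "PRU mean difference = 102" with an SD of 54. It then halves the effect: "we can calculate the sample size based on 50% reduced mean difference (PRU = 51). Then, we estimate 11 subjects". An equal placebo group and a 10% allowance lead to a target of 24.

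**The concern.** A trial with one primary hypothesis needs one variable on which it is tested. Here the two candidates exchange places between sections, so a reader cannot tell which result decides the trial. Either could later be reported as the pre-specified primary, with a sentence of the protocol to cite. The document gives no ordering of the two and no multiplicity rule.

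The second problem is sizing. If Section F governs, the calculation in Section B is for what has become a secondary variable, and the primary endpoint has no sample-size basis. With complete data planned for only 22 subjects and many platelet markers measured, a single fixed primary is the main protection against selective reporting.

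**Working it through.** **1. Status of each endpoint, side by side**

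| Response (assay, from Section E) | Section B | Section F |
|---|---|---|
| ADP (P2Y12 / PRUtest, PRU) | Primary | Secondary |
| Thrombin-like peptide (IIb/IIIa) | Secondary | Primary |
| Arachidonic acid (Aspirin) | Secondary | Secondary |

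The first two rows conflict in both directions. This is not two names for one assay, because Section E lists them as separate tests with separate agonists. Nor does it help that Section B speaks of a measurement and Section F of a hypothesis, since Section F moves ADP to the secondary level by name.

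**2. What the sample size covers**

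Inputs from Section B: difference 102 or 51 PRU, SD 54 PRU, two-sided alpha 0.05, power 0.80, one-group paired t-test. The noncentrality is (difference / SD) × √n on n − 1 degrees of freedom, with exact power from the noncentral t distribution.

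- Difference 102: 102/54 = 1.889. With n = 5, 1.889 × √5 = 4.22 and power is 0.878. With n = 6, power is 0.954. The stated 6 is one more than the minimum.
- Difference 51: 51/54 = 0.944. With n = 11, 0.944 × √11 = 3.13 and power is 0.806. With n = 10, power is 0.757. The stated 11 is reproduced.
- Total: 2 × 11 = 22. With 10% loss, 22/0.9 = 24.4, close to the stated 24.

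Every input is in PRU, so the calculation applies to the ADP endpoint only.

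**3. What can be said for thrombin-peptide**

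The document gives no expected difference and no SD for VerifyNow IIb/IIIa, so neither n nor power can be computed. In standardized terms, 11 subjects give 80% power for a paired effect of about 0.94 SD of the change, and 11 per group give 80% power for a between-group effect of about 1.26 SD. Nothing in the document shows whether the thrombin-peptide response would reach either.

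**4. Error rate if either endpoint may serve as primary**

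Assumption: both are tested two-sided at 0.05 and a positive result on either is claimed.

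- Independent tests: 1 − 0.95² = 0.0975.
- Bivariate normal test statistics: about 9.1% at correlation 0.5 and 7.0% at 0.9, falling to 5% at correlation 1.
- False reductions only (0.025 per test): 1 − 0.975² = 0.049 if independent, falling to 2.5% at correlation 1.

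The document does not give the correlation between the two assays, so the ranges are 5% to 9.75% for any false positive and 2.5% to 4.9% for a false reduction.

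**The case against.** No reading reconciles the two sections. The objections that can fairly be made concern what follows from the conflict.

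- **Section B also claims power for secondary measures.** It says 24 subjects should give at least 80% power for these, and VerifyNow IIb/IIIa is on that list. One of the figures it cites is a P-selectin response to thrombin. However, all the figures there are P-selectin, by flow cytometry or ELISA. None is a VerifyNow IIb/IIIa result, so the claim does not size that endpoint.
- **The error rate is hypothetical.** Each section names one primary, and neither plans to test two. A sponsor choosing the favourable result would choose a reduction, for which the independent-case figure is 4.9%, not 9.75%. This stands. The range describes what the ambiguity allows; it is not the plan's actual error rate, and the document does not show any intent to select.
- **ADP is probably what was meant.** Section B treats it as primary throughout, and Section F departs from this in two sentences. That is plausible and makes the repair easy, but the text does not settle it.
- **PRU is itself only partly covered.** The sizing is for the within-group paired test, while Section B also plans a between-group t-test. If SD 54 is assumed for the change in each arm, 11 per arm gives between-group power of about 0.56 at a difference of 51, and about 19 per arm would be needed for 80%. This is correct. It is a separate matter that naming the variable will not resolve.

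**Conclusion.** The concern holds and must be fixed. The current text names two different primary endpoints, each secondary in the other section. The only sample-size calculation is for ADP-stimulated PRU: 11 per group at a difference of 51 and SD 54, paired power 0.806. If Section F governs, the primary endpoint has no sample-size basis, and the size of any shortfall cannot be stated because the document gives no inputs for that assay.

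The contradiction rests on the text alone. Only the error-rate ranges need assumptions: that both endpoints are tested at 0.05, that either may be claimed, and that they are not negatively correlated.

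**What to change.** Name one primary variable, use it in both Sections B and F, and record the choice before unblinding.

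- **If ADP is intended**, which is the simplest route because the sample size rests on it: rewrite Section F so that the primary hypothesis is a reduction in ADP-stimulated PRU on VerifyNow P2Y12/PRUtest, with the thrombin-peptide (IIb/IIIa) and arachidonic-acid responses secondary. The cost is wording in one section. Section E already plans all three assays, so no extra patients, blood draws or data are needed.
- **If thrombin-peptide is intended**: change the primary and secondary lists in Section B and replace the sample-size justification with a difference and SD for VerifyNow IIb/IIIa. This may change the number of subjects.
- **If both are to be kept as primary**: state the multiplicity rule and size the trial for both.

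The same edit should say whether the paired or the between-group comparison is the primary test, since the present sizing supports only the paired one.
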